# 7.3.7. Epworth Sleepiness Scale (ESS)

The ESS is a self-administered questionnaire comprised of eight questions that provides a measure of a patient's general level of daytime sleepiness (Johns, 1991). The ESS asks respondents to rate, on a 4-point Likert scale (0-3), their usual chances of dozing off or falling asleep in different situations or activities that most people engage in as part of their daily lives. The total ESS score is the sum of 8 item scores and can range between 0 and 24 with a higher score indicating a higher level of daytime sleepiness. Most people can complete the ESS without assistance in 2 or 3 minutes.

ESS will be assessed at each visit.

## 7.3.8. Total Functional Capacity (TFC) of the UHDRS®

The UHDRS®-TFC scale is a tool used by clinicians to assess the stage of HD and the level of functional capacity in patients on five items: patients' ability to work, manage finances, run a house, take care of themselves, and live at home independently. The TFC score ranges from 0 (worse) to 13.

TFC will be assessed at screening (Visit 0), at the inclusion (Visit 1), and at the end of maintenance dose (Visit 5 at end of Week 10).

# 7.3.9. Functional Assessment (FA) of the UHDRS®

The UHDRS®-FA scale includes 25 yes/no questions about common daily tasks (range 0-25).

FA will be assessed at screening and at the end of the maintenance dose (Visit 5 at end of Week 10).

## 7.3.10. Barnes Akathisia Rating Scale (BARS)

The BARS (Barnes 1989) is administered by healthcare providers to assess the severity of druginduced akathisia and is scored as follows: Objective Akathisia, Subjective Awareness of Restlessness and Subjective Distress Related to Restlessness are rated on a 4-point scale from 0-3 and are summed yielding a total score ranging from 0 to 9. Then Global Clinical Assessment of Akathisia uses a 5-point scale ranging from 0-4.

BARS will be assessed at inclusion and at end of the maintenance dose (Visit 5 at end of Week 10).

## 7.3.11. Montreal Cognitive Assessment (MoCA) scale

The MoCA scale is a brief screening instrument recommended for the detection of mild cognitive impairment that is sensitive to executive dysfunction in a variety of neurological conditions (Mestre et al, 2018). When used in HD, it was more sensitive to detect mild to moderate cognitive impairment (Mickes et al, 2010; Videnovic et al 2010; Gluhm et al, 2013).

The items of the MoCA examine attention and concentration, executive functions, memory, language, visuo-constructional skills, conceptual thinking, calculations, and orientation.

The attention/executive function items include Trail Making Test B, digit span, target detection, verbal fluency, abstraction, and serial seven subtraction. The visuospatial items include clock drawing and cube copying. The language items include object naming and sentence repetition. The memory items include recall of five previously presented words. The orientation items include six orientation-based questions.

MoCA will be assessed at inclusion and at end of the maintenance dose (Visit 5 at end of Week 10).

## 7.3.12. Problem Behavior Assessment short form (PBA-s)

The PBA short form is the recommended outcome measure for behavioral symptoms in HD (Carlozzi et al, 2014). It is a semi-structured interview containing 11 items, each designed to measure the severity and frequency of behavioral neuropsychiatric symptoms that are frequent in HD: depression, suicidal ideation, anxiety, irritability, aggressive behavior, apathy, obsessive-compulsive symptoms, perseverative thinking, paranoid thinking, hallucinations, and disorientation.

Severity and frequency during the previous 4 weeks are rated separately for each symptom on a 5 point (0–4) scale.

PBA-s will be assessed at inclusion, at the interim visit (Visit 3 at the end of Week 6), and at the end of the maintenance dose (Visit 5 at the end of Week 10).

## 7.4. SAFETY REPORTING

## 7.4.1. Definitions

# 7.4.1.1. Adverse Event (AE)

The term Adverse Event covers any sign, symptom, syndrome, or illness which appears or worsens in a patient during the observation period in the clinical study, and which may impair the patient's well-being.

The term also covers laboratory findings or results of other diagnostic procedures which are considered to be clinically relevant (e.g. requiring unscheduled diagnostic procedures or treatment measures, or result in withdrawal from the study).

An AE may be:

- A new illness.
- The worsening of a sign, or symptom of the condition under treatment, or of a concomitant illness. Associated symptoms of Huntington's Disease (such as akathisia or dystonia) should not be considered as AEs except if they increase in terms of intensity and/or frequency.
- A known effect of the study medication (as listed in the SmPC).
- A combination of two or more of these factors.

No causal relationship with the study medication or with the clinical study itself is implied by the use of the term "Adverse Event."

## 7.4.1.2. Serious Adverse Event (SAE) or Serious Adverse Drug Reaction (Serious ADR)

A serious AE or drug reaction or any untoward medical occurrence that, at any dose, has one or more of the following attributes:

- Results in death.
- **Is life-threatening,** which means that the patient is at immediate risk of death at the time of the SAE; it does not refer to a SAE that hypothetically might have caused death if it was more severe.
- Requires inpatient hospitalization or prolongation of existing hospitalization. Hospitalization is defined as inpatient care that covers more than one calendar day.
- **Results in persistent or significant disability/incapacity**, which means that there is a substantial disruption of a person's ability to carry out normal life functions.
- Is a congenital anomaly/birth defect.
- Is medically important, defined as an event that may jeopardize the patient or may require medical or surgical intervention to prevent one of the outcomes listed above, or result in urgent investigation. Examples of such medical events include allergic bronchospasm requiring intensive treatment in an emergency room or at home, blood dyscrasias or convulsions that do not result in patient hospitalization.

# 7.4.1.3. Treatment-Emergent Adverse Event (TEAE)

A treatment-emergent adverse event (TEAE) is defined as any event not present prior to the initiation of the study treatment, or any event already present which worsens either in intensity, or frequency following the exposure to the study treatment.

## 7.4.1.4. Suspected Adverse Reaction

A suspected adverse reaction is any AE for which there is a reasonable possibility that the drug caused the AE. For the purposes of safety reporting, "reasonable possibility" means there is evidence to suggest a causal relationship between the drug and the AE. A suspected adverse reaction implies a lesser degree of certainty about causality than adverse reaction, which means any AE caused by a drug.

## 7.4.1.5. Adverse Reaction

An adverse reaction means an AE that is caused by a drug. Adverse reactions are a subset of all suspected adverse reactions that conclude the drug caused the event.

# 7.4.1.6. Unexpected Adverse Event or Suspected Adverse Reaction

An adverse reaction or suspected adverse reaction is considered "unexpected" if the nature or severity of it is not consistent with the applicable product information (e.g. Investigator Brochure Reference Safety Information or Summary of Product Characteristics, as applicable).

## 7.4.2. Procedures for recording, analyzing and reporting AEs

# 7.4.2.1. Monitoring and recording of AEs

At each visit, occurrence of AEs will be assessed by verbally asking the patients if they have had any problems or symptoms since their last visit.

For each AE, regardless of the suspected causal relationship to study drug, the Investigator has to report on the AE page(s) of the eCRF the relevant information of the AE including the nature, the anteriority (emergent or not), the timing of event occurrence and resolution, the frequency (intermittent or continuous), the severity (mild, moderate, severe), the relationship with the study drug, and actions taken to treat the adverse experience. The Investigator has also to pursue and obtain adequate information in order to determine the outcome of the AE and also to assess the seriousness, i.e. whether it meets the criteria for classification as a SAE requiring immediate notification to the Sponsor.

Whenever possible, a unifying diagnosis should be recorded in the eCRF as the AE rather than individual signs or symptoms. Similarly, the unifying diagnosis should be recorded as the AE rather than the abnormal laboratory result (i.e. "anemia" instead of "low hemoglobin"). If the AE is a worsening of a past medical condition, the AE should clearly indicate that the past medical condition has worsened using words such as "worsening," "aggravated," or "exacerbation."

AEs will be coded according to the Medical Dictionary for Regulatory Activity (MedDRA current version). AEs will be individually listed per patient number, presenting System Organ Class (SOC), preferred term, emergence, description, date and time of onset, date and time of last study drug administration before AE, duration, time from onset since last study drug administration, frequency, severity and seriousness, relationship to study drug, the required action taken (corrective treatment, hospitalization), and outcome if any.

All AEs (including SAEs) must be followed until satisfactory resolution or stabilization.

Any AE and any measure taken and follow-up result must be recorded in the patient's eCRF, as well as in the patient's source document. Follow-up laboratory results should be filed with the patient's source documentation.

## 7.4.2.2. Analysis and classification of AEs

#### **Assessment of Severity**

An assessment of the relative severity (or intensity) of an adverse experience is based on the Investigator's clinical judgment by using the following scale. The **maximum** severity encountered during the evaluation period should be checked. The assessment of severity should be independent of the assessment of the seriousness of the AE.

- Mild: No significant interference with the patient's usual activities, easily tolerated.
- **Moderate:** moderate interference with the patient's usual activities.
- **Severe:** major interference with the patient's usual activities, considered as unacceptable by the physician, or required specific treatment or required discontinuation from the study.

#### **Assessment of Causality**

The Investigator will make clinical judgement to determine whether or not, in their opinion, there is a reasonable possibility that the drug caused the adverse event

- Related/likely: Clearly related to the investigational agent/procedure, i.e. an event that follows a
  reasonable temporal sequence from administration of the study intervention, follows a known or
  expected response pattern to the suspected intervention, that can be confirmed by improvement
  on stopping and reappearance of the event after rechallenge and that could not be reasonably
  explained by the known characteristics of the patient's clinical state.
- Possibly related/Possible: Follows a reasonable temporal sequence from administration of the study intervention, follows a known or expected response pattern to the suspected intervention, but that could readily have been produced by a number of other factors.
- **Not related/Unlikely:** Clearly and incontrovertibly due only to extraneous causes, and does not meet criteria listed under possible (possibly related) or likely (related).

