#### 2.2.3. Assessment of Potential Risks and Benefits

Patients could benefit from treatment with SOM3355, which is known to reduce chorea symptoms as shown in the previous Phase 2a study, and it will be assessed as the primary endpoint.

SOM3355 is a well-known drug which has proven its good safety profile since more than 25 years of use as hypertensive drug. It has no warning regarding neuropsychiatric side effects and it was also well tolerated in the previous trial in HD patients, with no worsening of depression or suicidality although the sample was very limited.

Safety will be carefully monitored along the trial, particularly the risk of depression and suicidality will be assessed at each visit by the physician through specific scales (Beck Depression Inventory and Columbia-SSRS). Patients with known depression should be treated and stabilized with antidepressant therapy. Patients with severe untreated or under-treated depression at screening, or presenting a risk of suicide (item on suicidality >0 in BDI scale) are excluded from this study, and if the risk of suicide arises during the trial the patient should be immediately withdrawn from the study.

The known effect of bevantolol as beta blocker may induce potential side effects such bradycardia or orthostatic hypotension. Patients with a history of, or current, hypotension or bradycardia (HR <50 bpm) at the screening will be excluded from the study. Hemodynamic parameters (HR and BP) will be carefully monitored during the study as well as the recording of ECG to assess any abnormality. Severe permanent bradycardia will be excluded.

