## 7.4.3. Reporting Serious Adverse Events (SAEs)

All SAEs occurring during study participation must be reported **immediately (within 24 hours)** to the Sponsor representative (or designee), and then to the governing IRB/IEC as required by the IRB/IEC, local regulations, and the governing health authorities.

Prompt notification of SAEs by the Investigator to the appropriate Sponsor contact for SAE receipt is essential so that legal obligations and ethical responsibilities towards the safety of other patients are met. Any Unexpected SAE which is attributed to investigational product (SUSAR) requires immediate notification to the regulatory agencies. The full report will be sent to the regulatory agencies within the regulatory timelines. The Sponsor should also expedite the safety reporting to all concerned investigator/institutions, to IEC/IRB and regulatory agencies according to the local regulatory timelines.

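### The three causality grades leave no category for a well-timed adverse event of a new kind, and they conflict with the protocol's own reasonable-possibility test and its definition of an unexpected reaction

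*Protocol*

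**What the plan says.** Protocol 7.4.2.2, Assessment of Causality, opens by asking the investigator to judge "whether or not, in their opinion, there is a reasonable possibility that the drug caused the adverse event". It then defines three grades.

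- *Related/likely*: plausible timing, a recognised or "expected response pattern to the suspected intervention, that can be confirmed by improvement" once the drug is withdrawn and by return after rechallenge, and no reasonable explanation in the patient's clinical state.
- *Possibly related/Possible*: the event "follows a known or expected response pattern to the suspected intervention, but that could readily have been produced by a number of other factors", and its timing is plausible.
- The negative grade, *Not related/Unlikely*, applies to an event that is "Clearly and incontrovertibly due only to extraneous causes, and does not meet criteria listed under possible (possibly related) or likely (related".

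Three other sections use the result.

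- Protocol 7.4.1.4 defines a suspected adverse reaction by reasonable possibility, which "means there is evidence to suggest a causal relationship between the drug and the AE". It sets no pattern condition.
- Protocol 7.4.1.6 calls a reaction unexpected if its nature or severity "is not consistent with the applicable product information".
- Protocol 7.4.3 states: "Any Unexpected SAE which is attributed to investigational product (SUSAR) requires immediate notification to the regulatory agencies".

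The relationship is entered on the eCRF for every AE (7.4.2.1). Where possible it also goes with the initial SAE report, using the grades already described (7.4.3.1). SAP 4.10.1 tabulates treatment-related TEAEs and treatment-related serious TEAEs but does not say which of the three grades count as related.

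**The concern.** A causality scale should give every event exactly one grade, and it should not decide in advance whether the event was expected. This scale does neither. It places a form of expectedness inside both positive grades, although 7.4.1.6 already assesses expectedness separately. It also sets the negative grade so high that it cannot take what is left over.

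The events most exposed are those a Phase IIb trial of a repositioned drug needs to find: well-timed events not previously linked to the drug. Bevantolol has long use as an antihypertensive, but here it is given as a VMAT2 inhibitor to a different population. If sites resolve the gap in different ways, SUSAR assessment and the treatment-related tables will partly reflect site habit.

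**Working it through.** No sample size, error rate or event count bears on this point. The check reads the definitions as logical conditions and traces the result.

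**Inputs (Protocol 7.4.2.2).** T = plausible timing. K = known or expected pattern. R = improvement on stopping and return on rechallenge. O = other factors could readily have produced the event. E = the patient's clinical state reasonably explains it. X = clearly due only to outside causes.

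**Definitions**

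- Related = T and K and R and not E (R mandatory on a strict reading, optional on a permissive one)
- Possible = T and K and O
- Not related = X and not (Related or Possible)

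**Cases**

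| Event | Related | Possible | Not related | Grade |
|---|---|---|---|---|
| T, K and O true; X false | fails if E holds | met | fails | Possible |
| X true; K false | fails | fails | met | Not related |
| T true; K false; X false | fails on K | fails on K | fails on X | **none** |
| T and K true; O, E and X false; no rechallenge | met only if R is optional | fails on O | fails on X | Related, or **none** if R is mandatory |

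The third row is the main gap. It does not depend on how the rechallenge words are read. The fourth row is a further gap that opens only on the strict reading. The protocol schedules no rechallenge, and under 5.7 a patient who discontinues receives no more study treatment, so R could rarely be shown.

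**Conflict with the protocol's own tests.** Take the third-row event and suppose there is some evidence of a causal link. Under the lead-in of 7.4.2.2 and under 7.4.1.4 it is a suspected reaction. Under 7.4.1.6 it can be unexpected in nature. Under 7.4.3, if serious, it is a SUSAR once attributed to the product. Yet no grade in 7.4.2.2 records that attribution. The passages give different answers for the same event.

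**Trace to the SAP.** Section 4.10.1 lists seven rows in the overall TEAE summary. Two depend on relationship (treatment-related, treatment-related serious), leaving 7 − 2 = 5 that do not. It lists seven incidence tables by SOC and PT. Two depend on relationship (TEAEs by relationship, related serious TEAEs), again leaving 5. The missing-data rules in SAP 4.1.2 cover visit values and partial dates but not a missing causality grade, so the handling of an ungraded event in those four outputs is undefined.

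**The case against.** The strongest reply is that the lead-in governs. It asks for clinical judgement on reasonable possibility, and the grades only illustrate the answer. An investigator who suspects the drug can choose *Possible* under that test. This stands in part: the text does not forbid attribution. But the eCRF and the SAE report record one of the three grades, and choosing *Possible* for a new kind of event means setting aside that grade's own definition.

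A reader might infer several stronger things that the documents do not support.

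- *That no event unexpected in nature can ever be a SUSAR.* This would hold only if the pattern in 7.4.2.2 meant listing in the product information. The protocol does not say so. An event absent from the product information may still fit what the drug's pharmacology predicts. Nor does 7.4.3 limit attribution to the investigator's grade.
- *That such events are pushed into* Not related. That grade has the strictest bar. The literal outcome is no grade.
- *That depression and suicidality cannot be attributed to SOM3355.* Protocol 2.2.3 does say of the drug that "It has no warning regarding neuropsychiatric side effects", and 2.2.1 does not anticipate these effects. But 1.1 and 2.1.2 state them as a risk of tetrabenazine and deutetrabenazine, SOM3355 is developed as a VMAT2 inhibitor, and 5.7 names severe depression and suicidal ideation among AEs that may end participation. An investigator could reasonably go either way, so they illustrate inconsistent grading and not impossible attribution.
- *That the safety signal is lost.* All SAEs go to the sponsor within 24 hours whatever the causality. Five of seven summary rows and five of seven incidence tables ignore relationship. C-SSRS, BDI and DSMB review do not depend on the grade.

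The rechallenge wording can also fairly be read as permissive, so it is a secondary point.

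**Conclusion.** The rule is wrong as written and not merely short of detail. The three grades are not exhaustive, and they contradict the reasonable-possibility test in the same section and in 7.4.1.4, as well as the separate treatment of expectedness in 7.4.1.6 and 7.4.3. A well-timed event of a new kind has no defined grade. It may be graded differently between sites, and it may be missed in SUSAR assessment and in the four relationship-based outputs of SAP 4.10.1. The claim is that it may be missed, not that it must be.

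The number of events affected cannot be estimated from the documents. The conclusion assumes that investigators apply the grade definitions as printed. Where they follow the lead-in instead, the practical effect shrinks, but the contradiction remains.

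**What to change.** Reconcile Protocol 7.4.1.4, 7.4.1.6, 7.4.2.2 and 7.4.3.

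1. *Possible*: remove the pattern condition. Define the grade as a reasonable possibility in the sense of 7.4.1.4, with plausible timing and another cause also possible.
2. *Related*: keep the known pattern and rechallenge as supporting evidence only, not as requirements.
3. *Not related/Unlikely*: define as no reasonable possibility that the drug caused the event, so that every event falls into exactly one grade.
4. Leave expectedness entirely to 7.4.1.6.
5. SAP 4.10.1: state which grades count as treatment-related and how a missing causality grade is handled.

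The cost is a few lines of protocol and SAP text, updated eCRF help text and a memo to sites. The downside is that a few more events will be graded possibly related.

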# **Assessment of Outcome**

For all AEs the outcome should be documented at the latest at the last visit according to the following criteria:

- Ongoing.
- **Recovered**: the patient has fully recovered with no observable residual effects.
- Recovered with sequelae: the AE has resulted in a permanent impairment.
- **Unknown:** the outcome of the AE is not known because the patient did not return for follow-up (lost to follow-up).
- **Death** if the patient died due to the AE.

If an AE is still ongoing at the last visit the patient must be followed-up until the outcome can be documented without using the "ongoing" assessment.

In case of sequelae a description of sequelae must be provided in the eCRF. When reporting a death, the Investigator should supply any additional requested information such as autopsy reports (if available) and final medical reports.

In order to ensure the safety of the patients, the Investigator should take appropriate measures to follow all AEs until clinical recovery is complete and laboratory results have returned to normal, or until the patient has recovered, or until death. This may imply that observations will continue beyond the last planned visit per protocol, and that additional investigations may be requested by the monitoring team as it may be asked by the Sponsor.

